[figure not shown]

**PROJECT SYNOPSIS**

Study Title	Comparative effects of moxonidine and bisoprolol on bone metabolism, vascular and cellular markers of aging, blood pressure in hypertensive postmenopausal women
Study Sponsor:	Autonomous Nonprofit Organization "Society of experts in innovative technologies in medicine" (ANO "OSO ITEM")
Principal Investigator	[name], MD, PhD, professor
Therapeutic area / indication	Cardiology, essential hypertension
Study objectives and goals	
Primary Objective:
 
To investigate the effect of moxonidine versus bisoprolol on collagen type 1 C-telopeptide in postmenopausal female patients with arterial hypertension and osteopenia.
 
Secondary Objectives:
 
 
1. To investigate the effect of moxonidine versus bisoprolol on bone metabolism and bone tissue density in postmenopausal female patients with essential hypertension and osteopenia.
 
2. To investigate the effect of moxonidine versus bisoprolol on the processes of cellular and vascular aging in postmenopausal female patients with essential hypertension and osteopenia.
 
3. To investigate efficacy of antihypertensive therapy with moxonidine versus bisoprolol in hypertensive postmenopausal women.
 

Study Design	
Randomized, open-label, interventional, comparative clinical trial
 
Study population is postmenopausal women with essential hypertension and osteopenia. The study will enroll 114 patients after screening (it is expected that 300 patients will need to be screened to reach this enrolment goal).
 
After the informed consent signing, the patient's participation in the study will include the period before the studied product administration, treatment period and a final visit.
 
Patients will be randomized to one of two groups: moxonidine group or bisoprolol group.
 
According to the study protocol, patients randomization to the control and investigated groups will be carried out using a simple envelopes method and, therefore, it is assumed that the control and the main groups will be matched by the basic measured parameters; the number of subjects in the main and control groups is planned to be equal.
 
The study endpoints are measured prior to the studied product initiation (V1) and after completion of 48-week treatment with the investigated product (V4).

	
The period prior to the studied treatment initiation is designed to assess the patient meeting inclusion criteria and to carry out 7-10-day washout period in patients with previous antihypertensive therapy. The planned duration of the period before the treatment initiation does not exceed 14 days after the signing of the informed consent form by the patient.
 
Then, at the enrollment visit during the treatment period, the investigator will assess the patient meeting the inclusion criteria. If the inclusion criteria are met, the patient will be enrolled in the study. The baseline condition data will be obtained from the patient, then the patient will be randomized to one of the two treatment groups (moxonidine or bisoprolol). The treatment period involves the enrollment visit (V1), and 3 more visits.
 
The final visit 4 is carried out at week 48 after the enrollment visit, the patient then completes the study.
 
The patients' treatment includes gradual titration of the studied products doses.
 
Group 1 will receive moxonidine with the dose titrated to a maximum, and then, if necessary, the patient will be shifted to the combination therapy (Step 2 – adding an ACE inhibitor)
 
Group 2 will receive bisoprolol with the dose titrated to a maximum, and then, if necessary, the patient will be shifted to the combination therapy (Step 2 – adding an ACE inhibitor).
 
After randomization to moxonidine and bisoprolol groups (V1), patients start treatment with 0.4 mg moxonidine QD or 5 mg bisoprolol QD. If the target BP (<140/90 mmHg) is reached in 2 weeks, the patient continues taking the medication at the same dose. If the target BP is not reached in 2 weeks, the moxonidine dose is increased to 0.6 mg QD, the dose of bisoprolol is increased to 7.5 mg QD. If the target BP is not reached in 2 weeks of treatment with the increased doses, an ACE inhibitor (perindopril) at a dose of 10 mg/day is added at the 8th week of the study. In case of intolerance to perindopril, losartan at a dose of 50 mg/day will be administered.
 
During the study, the patient will have parameters of efficacy, tolerability and safety of the therapy with moxonidine or bisoprolol regularly assessed.

Study Groups	
Investigated group: postmenopausal women with essential hypertension and osteopenia treated with moxonidine.
 
Comparative group: postmenopausal women with essential hypertension and osteopenia treated with bisoprolol.

Randomization procedure	Simple randomization using the method of envelopes
Number or patients	114 patients.
Screening inclusion criteria	
 
1. Female with age 45 years and older.
 
2. Postmenopausal (absence of menstrual periods for a minimum of 12 months) at the moment of Informed Consent sign.
 
3. Arterial hypertension grade I / II per ESH/ESC 2013
 

	
guidelines (diastolic pressure <math>\geq 90</math> and <math><110</math> mm Hg, systolic pressure <math>\geq 140</math> and <math><180</math> mm Hg).
 
4. Not achieving BP targets <math><140/90</math> mmHg either during antihypertensive therapy or naive.
 
5. Absence of moxonidine or bisoprolol treatment at least 6 months before the study
 
6. Osteopenia of lumbar spine and/or proximal part of the femur (osteoporosis T-score from -1 to -2.5 standard deviations [SD]) by X-Ray densitometry.
 
7. Signed Informed Consent for participation in the study.


Screening exclusion criteria
	
 
1. Hypersensitivity to moxonidine, bisoprolol or any other ingredient of the respective formulations
 
2. Any Contraindications for moxonidine, bisoprolol
 
3. Osteoporosis (T-score below - 2.5 SD).
 
4. Primary or secondary hyperparathyroidism.
 
5. Paget's disease of bones.
 
6. History of low traumatic bone fractures.
 
7. Malabsorption syndrome.
 
8. History of gastro-intestinal surgery.
 
9. Severe disturbance of peripheral circulation.
 
10. Raynaud's disease.
 
11. Symptomatic (secondary) hypertension (caused by any primary internal diseases)
 
12. Morbid obesity (BMI over 40 kg/m^2).
 
13. Symptoms of estrogen deficiency such as hot flushes, night sweats, vaginal dryness
 
14. Administration of any hormone-replacement therapy (HRT) or intake of isoflavones
 
15. Secondary hypogonadism.
 
16. Systolic BP <math>\geq 180</math> mm Hg and/or Diastolic BP <math>\geq 110</math> mm Hg.
 
17. Clinical presentations of cardiovascular disease: coronary heart disease (CHD), history of stroke, transient ischemic attack (TIA), Charcot's syndrome.
 
18. Severe heart failure.
 
19. Hemodynamically significant congenital heart disease.
 
20. Heart rhythm disorders which require permanent use of any antiarrhythmic medications (including <math>\beta</math>-adrenoblockers and calcium antagonists).
 
21. Diabetes mellitus of any genesis.
 
22. Severe liver failure.
 
23. Severe kidney failure including patients on dialysis
 
24. Thyroid diseases accompanied by functional disorders (thyrotoxicosis or uncompensated hypothyroidism).
 
25. Alcohol and drug abuse.
 
26. Patients with oncological diseases diagnosed within 5 years before IC execution.
 
27. Inability of the patient to comprehend the essence of the program and to provide his/her consent for participation
 

	
in the program.
 
28. Patients with any condition, which in the opinion of the Investigator makes the patient unsuitable for inclusion based on clinical judgment.
 
29. Corticosteroid therapy
 
30. Participation in any other clinical study during the whole course of this investigation including participation in a study within 30 days prior to providing the informed consent for this trial


Start of treatment criteria
	
1) Patient is to meet all the inclusion criteria and should lack any of the exclusion criteria.
 
2) Patients previously treated with antihypertensive agents have undergone 7-10-day washout period according to the protocol (all antihypertensive drugs are discontinued, except fast-acting agents to relieve hypertensive episodes).

Duration of the study
	
Patients' enrollment – 12 months.
 
The total duration of the study is 48-50 weeks. (Screening period (1-14 days) and washout period (7-10 days), every patient will be treated for up to 48 weeks).
 
FPFV – Q1.2015          LPFV – Q1.2016          LPLV – Q1.2017            CSR – Q3.2017

Investigated product.  Dose, method of administration
	
Film-coated tablets of Moxonidine (Physiotens) manufactured by Rottendorf Pharma GmbH, Germany, packaged and released by Abbott Healthcare SAS, France.
 
One tablet contains 0.40 mg moxonidine as an active substance and the following excipients: lactose monohydrate - 95.60 mg; povidone K25 - 0.70 mg; crospovidone – 3.00 mg; magnesium stearate - 0.30 mg; hypromellose 6mPas - 1.300 mg; ethyl cellulose aqueous Disp.30% - 4.000 mg (solids 1.200 mg) ; macrogol 6000 - 0.250 mg; talc - 0.875 mg; red ferric oxide (E172) - 0.125 mg; titanium dioxide (E171) - 1.250 mg. There are 14 tablets in the blister; the carton contains 1, 2 or 7 blisters.
 
One tablet contains 0.20 mg moxonidine as an active substance and the following excipients: lactose monohydrate - 95.80 mg; povidone K25 - 0.70 mg; crospovidone – 3.00 mg; magnesium stearate - 0.30 mg; hypromellose 6mPas - 1.300 mg; ethyl cellulose aqueous Disp.30%- 4.000 mg (solids 1.200 mg); macrogol 6000 - 0.250 mg; talc - 0.9975 mg; red ferric oxide (E172) - 0.0025 mg; titanium dioxide (E171) - 1.250 mg. There are 14 tablets in the blister; the carton contains 1, 2 or 7 blisters.

	
Moxonidine is taken orally, once or twice a day, regardless of meals.          Maximum daily dose of moxonidine is 0.6 mg.
 
Duration of treatment: Moxonidine 0.4 mg is prescribed to postmenopausal patients with hypertension and osteopenia once or twice a day. Subsequently, in patients with no response, the daily dose is titrated up to 0.6 mg QD; then perindopril 10 mg may be added to the regimen at week 8, if necessary. In case of intolerance to perindopril, losartan at a dose of 50 mg/day will be administered.


Comparative product.
 
Dose, method of administration
	
Bisoprolol, film-coated tablets
 
One tablet contains bisoprolol hemifumarate and bisoprolol fumarate (2: 1) as active substances 5 mg, and the following excipients: calcium hydrogen phosphate anhydrous - 132 mg; corn starch fine powder - 14.5 mg; colloidal anhydrous silica - 1.5 mg; MCC - 10 mg; crospovidone - 5.5 mg; magnesium stearate - 1.5 mg
 
film coating: hypromellose 2910/15 - 2.2 mg; macrogol 400 - 0.53 mg; dimethicone 100 - 0.11 mg; iron oxide yellow dye (E172) - 0.02 mg; titanium dioxide (E171) - 0.97 mg.
 
Bisoprolol is taken orally, once a day, regardless of meals.          Bisoprolol 5 mg is prescribed to postmenopausal patients with hypertension and osteopenia. Subsequently, in patients with no response, the daily dose is titrated up to 7.5 mg every 2 weeks; then perindopril 10 mg may be added to the regimen at week 8, if necessary. In case of intolerance to perindopril, losartan at a dose of 50 mg/day will be administered.

Other agents allowed by the protocol
	
Losartan film-coated tablets produced by Berlin-Chemie, Germany.
 
Each tablet contains 50 mg of losartan.
 
Losartan is taken orally, once a day, regardless of meals. The product is prescribed to postmenopausal patients with hypertension and osteopenia non-responsive to moxonidine or bisoprolol monotherapy for 4 weeks and intolerant to perindopril.
 
Calcium carbonate + cholecalciferol, chewable tablets          Each tablet contains the following active ingredients calcium carbonate 1250 mg (equivalent to 500 mg of elemental calcium), cholecalciferol (vitamin D3) 5 mcg (200 IU) (as cholecalciferol concentrate - 2 mg).
 
excipients: sorbitol - 390 mg; isomalt - 62 mg; povidone - 36.4 mg; magnesium stearate - 6 mg; aspartame - 1 mg; orange oil - 0.97 mg; mono- and diacylglycerols - 0.0008 mg.
 
The product is taken orally during meals, it should be chewed or dissolve in the mouth.


Endpoints
	
Primary endpoint:
 
Changes in mean values of the bone resorption marker (collagen type 1 C-telopeptide) at the end of the study (V4) from the baseline (V1) in comparison between the groups.
 
Secondary endpoints:
 
 
1) To assess mean values of osteocalcin at visit 4 versus baseline level (visit 1) and comparison between the groups
 
2) To assess mean values of the receptor activator of nuclear factor kappa-B ligand (RANKL) at visit 4 versus baseline level (visit 1) and comparison between the groups
 
3) To assess mean values of BMD at visit 4 versus baseline level (visit 1) using control dual-energy X-ray absorptiometry and comparison between the groups
 
4) To assess mean telomerase activity at visit 4 versus baseline level (visit 1) and comparison between the groups
 
5) To assess mean pulse wave velocity (PWV) at visit 4 versus baseline level (visit 1) and comparison between the groups
 
6) To assess mean intima-media thickness (IMT) at visit 4 versus baseline level (visit 1) and comparison between the groups
 
7) To estimate the proportion (%) of patients who achieved target blood pressure <140/90 mmHg at the visit 2 (week 8), visit 3 (week 24) and 4 (Week 48) and according to the patient's diary.
 

Evaluation of pharmacokinetic / pharmacodynamic parameters
	
The parameters will not be evaluated

Evaluation of quality of life / pharmacoeconomic parameters
	
The parameters will not be evaluated

Statistical Analysis
	
Efficacy Analysis:
 
Changes in mean values of the bone resorption marker (collagen type 1 C-telopeptide) at the end of the study (V4) from the baseline (V1) are evaluated in comparison between the groups.
 
Changes in mean values of the receptor activator of nuclear factor kappa-B ligand (RANKL) at visit 4 versus baseline level (visit 1) in comparison between the groups.
 
Changes in mean values of BMD at visit 4 versus baseline level (visit 1) using control dual-energy X-ray absorptiometry and in comparison between the groups.

	
Changes in mean telomerase activity at visit 4 versus baseline level (visit 1 in comparison between the groups).
 
Changes in mean pulse wave velocity (PWV) at visit 4 versus baseline level (visit 1) and in comparison between the groups.
 
Changes in mean intima-media thickness (IMT) at visit 4 in comparison between the groups.
 
The efficacy of the investigated treatment is estimated based on whether target blood pressure (<140/90 mm Hg) at visits V2, V3 and V4 is reached.
 
Safety Analysis:
 
Adverse events (AEs) are recorded at every visit. Analysis of adverse events and serious adverse events is conducted to determine the total number of AEs, the total number of patients with adverse events, the number of treatment-related adverse events, the number of AEs associated with product discontinuation and the number of voluntary withdrawal of informed consent.
 
Rate and severity of all adverse events and drug-related adverse events (i.e., at least “possibly” associated with the studied product) will be summarized by organ systems. Data on the product withdrawal due to adverse events will be summarized in tables.
 
Statistical methods:
 
Statistical analysis will be conducted under the supervision of a responsible biostatistician. The details of statistical analysis will be provided in the statistical analysis plan in accordance with the GCP requirements and other relevant requirements and laws. The statistical analysis plan will be finalized before the data lock point. All deviations from the final statistical plan version will be justified in the final program report.
 
The results will be combined for the complete study sample. Two-sided levels of significance and confidence intervals will be calculated. The significance of differences will be calculated for two-sided tests, with a critical significance level of 0.05.
 
For parameters of interval scale type, the following will be calculated: the arithmetic mean (95% confidence interval for the mean), standard deviation, median, 25th and 75th percentiles. For parameters of ordinal scale type, median, 25th and 75th percentiles will be calculated. For parameters of nominal scale type, frequency categories and confidence intervals for the frequencies (modified Wald method) will be calculated. If the assumptions made during the preliminary study planning are found to be erroneous, the analysis methods will be modified to conduct a more suitable analysis. The result of the primary endpoint analysis will be presented as an absolute number and

--	---------------------------------------------------------------------------------------------------------------------------------------------------------------------------------------------------------------------------------------------------------------------------------------------------------------------------------------------------------------------------------------------------------------------------------------------------------------------------------------------------------------------------------------------------------------------------------------------------------------------------------------------------------------------------------------------------------------------------------------------------------------------------------------------------------------------------------------------------------------------------------------------------------------------------------------------------------------------------------------------------------------------------------------------------------------------------------------------------------------------------------------------------------------------------------------------------------------------------------------------------------------------------------------------------------------------------------------------------------------------------------------------------------------------------------------------------------------------------------------------------------------------------------------------------------------------------------------------------------------------------------------------------------------------------------------------------------------------------------------------------------------------------------------------------------------------------------------------------------------------------------------------------------------------------------------------------------------------------------------------------------------------------------------------------------------------------------------------------------------------------------------------------------------------------------------------------------------------------------------------------------------------------------------------------------------------------------------------------------------------------------------------------------------------------------------------------------------------------------------------------------------------------------------------------------------------------------------------------------------------------------------------------------------------------------------------------------------

	
proportion (%) of patients with target BP (<140/90 mm Hg) achieved at visit V4. Statistical analysis will be carried out using SPSS / PASW Statistics software package (version 18), SPSS Inc., Chicago, Illinois, USA.
 
Rationale for sample size As this is an explorative study with open design no formal sample size calculation was performed. The focus of the study is to obtain scientific data for a publication and taking into account a reason of feasibility of enrollment to timelines and screening of 300 patients per year in assumption that ratio of screened / enrolled patients is approximately 3 to 1 so it is expected that not less than 100 patients but no more than 114 patients will be enrolled in the study. According to this approach the total sample size is chosen 114 subjects.

--	------------------------------------------------------------------------------------------------------------------------------------------------------------------------------------------------------------------------------------------------------------------------------------------------------------------------------------------------------------------------------------------------------------------------------------------------------------------------------------------------------------------------------------------------------------------------------------------------------------------------------------------------------------------------------------------------------------------------------------------------------------------------------------------------------------------------------------------------------

LIST OF ABBREVIATIONS AND DEFINITION OF TERMS

ACEI - angiotensin-converting enzyme inhibitor

AE - adverse event

ALT - alanine aminotransferase

AR - adverse reaction

AST - aspartate aminotransferase

BB - beta-blockers

BMD - bone mass density

BMD - bone mineral density

BP - blood pressure

CHD - coronary heart disease

CRF - case report form

CTX - collagen type 1 C-telopeptide

CVD - cardiovascular disease

DBP - diastolic blood pressure

ECG - electrocardiogram

HCF - health care facility

HR - heart rate

HTN - hypertension

IMT - intima-media thickness

OC - osteocalcin

OPG - osteoprotegerin

PWV - pulse wave velocity

RANKL - Receptor activator of nuclear factor kappa-B ligand

SAE - serious adverse event

SBP - systolic blood pressure

TIA - transient ischemic attack

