Group 2 will receive bisoprolol with the dose titrated to a maximum, and then, if necessary, the patient will be shifted to the combination therapy (Step 2 – adding an ACE inhibitor).

After randomization to moxonidine and bisoprolol groups (V1), patients start treatment with 0.4 mg moxonidine QD or 5 mg bisoprolol QD. If the target BP (<140/90 mmHg) is reached in 2 weeks, the patient continues taking the medication at the same dose. If the target BP is not reached in 2 weeks, the moxonidine dose is increased to 0.6 mg QD, the dose of bisoprolol is increased to 7.5 mg QD. If the target BP is not reached in 2 weeks of treatment with the increased doses, an ACE inhibitor (perindopril) at a dose of 10 mg/day is added at the 8th week of the study. In case of intolerance to perindopril, losartan at a dose of 50 mg/day will be administered.

During the study, the patient will have parameters of efficacy, tolerability and safety of the therapy with moxonidine or bisoprolol regularly assessed.

The study design is shown in Figure 1.

Figure 1. The overall study design

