### **Treatment regimens**

- **Group 1** patients receive moxonidine with dose titration up to the maximum, then a patient may be switched to the combination therapy, if necessary (step 2 - adding an ACE inhibitor).
- **Group 2** patients receive bisoprolol with dose titration up to the maximum, then a patient may be switched to the combination therapy, if necessary (step 2 - adding an ACE inhibitor).

The investigator will provide a Group 1 patient with moxonidine 0.4 mg in the amount required for 56 days of treatment plus 7 extra days and additionally moxonidine 0.2 mg in an amount required for 42 days of treatment if the dose is titrated up to 0.6 mg/day.

The patient will take the first moxonidine tablet immediately during the visit after all the visit procedures are completed. The patient will be instructed to take 1 tablet of moxonidine 0.4 mg in the morning, daily. The next visit will be scheduled in week 8 after the enrollment visit (in 56 days  $\pm$  5 days after the enrollment visit).

The patient will be asked to bring all the blisters of investigated product (empty, started and not started blisters) to every visit after the study initiation.

The investigator will give the patient blood pressure self-monitoring diary which is to be used by the patient to daily document her BP values and to bring it to every subsequent visit.

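### One-tablet-a-day instructions do not fit titrated patients in either arm, and the synopsis frequency for moxonidine 0.4 mg conflicts with once-daily dosing elsewhere

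*Combined protocol and SAP*

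**What the plan says.** **Frequency.** The synopsis row on the investigated product gives the trial prescription as "Moxonidine 0.4 mg is prescribed to postmenopausal patients with hypertension and osteopenia once or twice a day". The same cell has a general administration line, "Moxonidine is taken orally, once or twice a day, regardless of meals", then the cap, "Maximum daily dose of moxonidine is 0.6 mg", and the titration step, "the daily dose is titrated up to 0.6 mg QD". The synopsis design row and 3.1 say that "patients start treatment with 0.4 mg moxonidine QD or 5 mg bisoprolol QD", and 3.1 adds that if target BP is not reached "the moxonidine dose is increased to 0.6 mg QD". At enrolment (3.6.2, Treatment regimens) the wording is "The patient will be instructed to take 1 tablet of moxonidine 0.4 mg in the morning, daily". Section 3.8.1 repeats the synopsis prescription sentence but with a once-daily frequency; its own general administration line also allows one or two intakes. Section 5.1 gives moxonidine once daily at both dose levels.

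**Tablet count.** Moxonidine is listed in 0.4 mg and 0.2 mg strengths (synopsis, 3.8.1). Bisoprolol is listed only as a 5 mg tablet (synopsis, 3.8.2), with titration to 7.5 mg once daily. At V1, moxonidine patients receive 0.4 mg tablets for 56 days plus 7 spare days and "additionally moxonidine 0.2 mg in an amount required for 42 days of treatment if the dose is titrated up to 0.6 mg/day". At V2 (3.6.4) and V3 (3.6.5) patients in both arms are told to take a single tablet of the supplied product each day. Section 5.1 repeats a one-tablet daily instruction for group 1 and again for group 2. None of these four lines has a variant for titrated patients.

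**The concern.** These are operative dosing instructions, not background text. A titrated patient who follows the V2 or V3 line exactly would take less than her assigned dose. The frequency wording in the synopsis row gives the investigational arm a regimen that the visit sections do not use.

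Tablet counts also have a second use. Compliance is judged from returned tablets (3.9.2, 5.5), and compliance below 80% is a listed ground for withdrawal (4.5). A percentage needs an expected number of tablets as its denominator, and the one-tablet wording gives the wrong number for titrated patients.

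**Working it through.** The check is dose arithmetic from the listed strengths and the visit calendar.

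**1. The plan's own figures reproduce.** The moxonidine maximum is 0.4 + 0.2 = 0.6 mg/day, that is, one tablet of each strength. The 0.2 mg supply runs from the week 2 telephone visit to V2: 56 − 14 = 42 days, as 3.6.2 states. The intended 0.6 mg regimen is therefore two tablets.

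**2. Tablets needed per daily dose.**

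| Assigned dose | Listed strengths | Tablets needed | Written instruction |
|---|---|---|---|
| Moxonidine 0.4 mg | 0.4, 0.2 mg | 1 | 1 |
| Moxonidine 0.6 mg | 0.4, 0.2 mg | 2 (0.4 + 0.2) | 1 |
| Bisoprolol 5 mg | 5 mg | 1 | 1 |
| Bisoprolol 7.5 mg | 5 mg | 7.5 / 5 = 1.5 | 1 |

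The instruction fits both starting doses and neither titrated dose.

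**3. Shortfall if the line were followed literally.** Moxonidine, one 0.4 mg tablet: (0.6 − 0.4) / 0.6 = 33%. Bisoprolol, one 5 mg tablet: (7.5 − 5) / 7.5 = 33%.

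**4. Period covered.** V2 is day 56, V3 day 168 and V4 day 336. The V2 line governs 168 − 56 = 112 days and the V3 line 336 − 168 = 168 days, together 280 of 336 days. Titration can start at week 2, so some patients may already be on the higher dose at V2.

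**5. Effect on an expected tablet count.** For a moxonidine patient on 0.6 mg from V2 to V3, the correct expected number is 2 × 112 = 224 tablets; the written instruction implies 112. A patient who took only one 0.4 mg tablet a day would score 112/112 = 100% against the second figure while receiving 0.4/0.6 = 67% of her dose.

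**6. Readings of the synopsis frequency sentence.**
- 0.4 mg per intake, twice: 2 × 0.4 = 0.8 mg/day, above the 0.6 mg maximum in the same cell.
- 0.4 mg as a daily total, split: 2 × 0.2 = 0.4 mg/day, within the maximum but not once daily.
- 0.4 mg and 0.2 mg at separate times: 0.6 mg/day, within the maximum but not once daily.

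Every reading that uses the second intake contradicts the once-daily regimen in the synopsis design row, 3.1, the prescription sentence of 3.8.1 and 5.1.

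**The case against.** The case for leaving the text alone has real force on several points.

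- **The general administration lines.** The dose-free lines in the synopsis and 3.8.1 can be read as general product posology, which the trial prescription then narrows. That stands. Only one sentence, in the synopsis, attaches a second intake to the trial's 0.4 mg dose.
- **The 0.8 mg/day reading.** A reader might infer that the synopsis permits 0.8 mg/day. The documents do not support this: the cap comes just before the sentence, and a daily dose that starts at 0.8 mg cannot be titrated up to 0.6 mg. What survives is a split dose, and no visit instruction implements one.
- **The moxonidine tablet count.** The V1 supply of extra 0.2 mg tablets shows the intended combination, so site staff could work it out. The group 1 line in 5.1 closes a paragraph on the starting dose and may describe only that dose, although the same paragraph refers to the whole study. This softens the point for moxonidine but does not remove it, because the V2 and V3 lines plainly cover titrated patients too.
- **Bisoprolol.** The inference is not available here. Section 3.6.2 has no matching supply line, and no second strength is listed.

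**Conclusion.** The plan is wrong as written on two matters of wording, and the point is minor. The one-tablet instructions in 3.6.4, 3.6.5 and 5.1 (both groups) do not fit titrated patients: moxonidine 0.6 mg takes two tablets and bisoprolol 7.5 mg takes one and a half of the only listed strength. The synopsis prescription sentence conflicts with once-daily dosing elsewhere.

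The 33% shortfall is what literal compliance would produce, not a forecast. It assumes that staff and patient disregard the recorded dose and, for moxonidine, the extra strength dispensed. The bisoprolol count assumes that no other strength is supplied; the documents list none and do not say whether tablets are to be halved.

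A reader might also infer that compliance withdrawals, and so the per-protocol population, would be distorted. The documents do not say what expected count sites will use, so that does not follow. No sample size, endpoint or analysis is affected.

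**What to change.** 1. **Synopsis, investigated product row:** change the prescription sentence to moxonidine 0.4 mg once a day (QD), in the morning. Align the general administration lines there and in 3.8.1 to once a day. Keep the 0.6 mg maximum and the titration step.
2. **Sections 3.6.4, 3.6.5 and 5.1 (groups 1 and 2):** replace the one-tablet wording with the assigned dose, once daily in the morning, made up as follows:
   - moxonidine 0.4 mg: one 0.4 mg tablet;
   - moxonidine 0.6 mg: one 0.4 mg plus one 0.2 mg tablet, taken together;
   - bisoprolol 5 mg: one 5 mg tablet;
   - bisoprolol 7.5 mg: one and a half 5 mg tablets, or name the additional strength supplied.
3. **Section 5.5:** count returned tablets against the number expected for the assigned dose.

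The cost is a wording amendment: three frequency phrases, four tablet-count lines and one sentence on compliance. Correcting the moxonidine text alone would leave the same mismatch in the comparator arm. Visits, doses, sample size and analysis stay as they are.
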